- Varies by system
- OUD-CDS implementation date through a predetermined time at which the Wizard interfaces will be turned off in the intervention clinics

Accrual Period

- Varies by system
- OUD-CDS implementation date through a predetermined time at which no more people will be included in the analytic sample

Index Date

- Varies by patient
- First visit at which the OUD-CDS identifies that the patient is study eligible

Observation Period

- Varies by patient
- Index visit date through a predetermined time at which outcome data will no longer be accumulated

H1.2: Patients previously diagnosed with OUD or identified as high risk by the OUD-CDS at an index visit will be more likely to have naloxone rescue kits ordered in the intervention clinics than in the UC clinics within 30 days post-index.

Aim 2. To assess the impact of OUD-CDS on important patient outcomes of initiation and maintenance of Medications for Opioid Use Disorder (MOUD) in patients identified as having OUD or being at high risk for OUD.

H2.1: Patients identified as having OUD or as being at high-risk for OUD by the OUD-CDS at an index visit will be more likely to have MOUD orders or referral for OUD treatment within 30 days post-index in intervention clinics than in UC clinics.

H2.2: Patients identified as having OUD or as being at high-risk for OUD by the OUD-CDS at an index visit will have significantly more days covered by a MOUD prescription at 90 days post-index in intervention clinics than in UC clinics.

Aim 3. To assess the long-term impact of OUD CDS on important patient outcomes in patients with OUD or identified as high risk for OUD.

H3.1: Patients with OUD or identified as high-risk for OUD by the OUD-CDS who are cared for in intervention clinics will have significantly fewer post-index emergency department (ED) visits during the observation period (i.e., the period between each patient's index date and last observation) compared to patients cared for in UC clinics.

H3.2: Patients with OUD or identified as high-risk for OUD by the OUD-CDS who are cared for in intervention clinics will have significantly fewer post-index hospitalizations during the observation period compared to patients cared for in UC clinics.

Aim 4. To describe and quantify costs of OUD-CDS implementation and maintenance and the short-term cost impacts of the OUD-CDS.

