H4.1: After controlling for demographics, baseline clinical status and prior costs of care, patients with OUD or identified as high risk for OUD by the OUD-CDS will have lower healthcare costs in intervention compared to UC clinics during the observation period (i.e., savings from lower ED visits and hospitalizations will outweigh increased costs of OUD treatment and naloxone rescue kits and OUD-CDS implementation and maintenance).

Aim 5. To use mixed quantitative and qualitative methods to identify, describe and quantify barriers and facilitators to implementation of the OUD-CDS so that it can be adapted to maximize its use and effectiveness.

Secondary Analyses: As secondary outcomes, we may assess whether patients with OUD or identified as high risk for OUD by the OUD-CDS who are cared for in intervention clinics have lower post-index rates of all cause death and of fatal or non-fatal opioid overdoses during the intervention period compared to similar patients in UC clinics. We will also assess OUD-CDS use rates for intervention clinics and assess whether the effectiveness of OUD-CDS varies as a function of site, clinic, provider or patient characteristics. Finally, we will assess whether PCP ratings of confidence in treating patients with OUD differ at 9 months between treatment groups, and how intervention PCPs rate satisfaction and acceptability of the OUD-CDS tool at 9 months.

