- % of patients at high risk for OUD provided a with naloxone rescue kit
- n of adult patients at clinic
- % of adult patients with government sponsored insurance
- % of adult patients who are non-Hispanic White
- n of waived providers

Each patient will be considered to belong to the clinic in which his or her first visit that is eligible for the OUD-CDS intervention (i.e., index visit) takes place, and as such will be in the treatment group to which their clinic was randomly assigned. Post-index visits may take place in the same or different clinics or treatment groups relative to the index visit and may or may not be eligible for the OUD-CDS to offer treatment recommendations. In keeping with an intent-to-treat principle, all index and post-index visits and outcome measures for each patient will be attributed to the treatment group assignment of the clinic where the index visit took place.

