10.4 Premature Withdrawal of Participants

Once randomized, all primary care clinics are anticipated to remain enrolled for the duration of the study. All PCPs in randomized clinics will be followed for the duration of the study unless they die or leave the employment of the clinic. All study-eligible patients with OUD or identified by the algorithms as being at high risk of OUD in randomized clinics will be followed for the duration of the study unless they die or leave the care system. Patients who have opted out of research will be excluded from all analyses.

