11.0 STUDY ASSESSMENTS

11.1 Table of Assessments

Table 1. Assessment of Primary, Secondary and Exploratory Outcomes

Outcome	Timing*	Data Source
OUD diagnosis	Index date, 30 days, 90 days	EHR/OUD-CDS data
Naloxone prescription	Index date, 30 days, 90 days	EHR/OUD-CDS & Claims data
MOUD orders or referral	Index date, 30 days, 90 days	EHR/OUD-CDS & Claims data
days covered by MOUD prescription	Index date, 30 days, 90 days	EHR data
ED visits	Observation period	EHR & Claims data
Hospitalizations	Observation period	EHR & Claims data
Health care costs	Observation period, with pre-observation period matched for number of days	EHR & Claims data
Costs of OUD-CDS implementation and maintenance	Mid-intervention period	Interviews/surveys with implementation site staff
All-cause mortality	Observation period	EHR data, Claims data, State mortality data
Opioid overdoses	Observation period	EHR & Claims data
OUD-CDS use rates	Intervention period	EHR/OUD-CDS data
PCP confidence in treating patients with OUD	Baseline, 9 months	PCP surveys
PCP ratings of likelihood to prescribe buprenorphine for patients with OUD should no waiver be required	Baseline, 9 months	PCP surveys
Intervention PCP ratings of OUD-CDS satisfaction and acceptability	9 months	PCP surveys
Waivered PCPs	Pre-intervention, intervention period	Administrative data
Buprenorphine prescriptions written by waivered PCPs	Intervention period	EHR/OUD-CDS data
Adherence to therapy	Intervention period	EHR/OUD-CDS data
Screening for comorbid conditions	Observation period	EHR/OUD-CDS data

*Definitions:
 
Index Date
 
 ▪ Varies by patient ▪ First visit at which the OUD-CDS identifies that the patient is study eligible 
Intervention Period
 
 ▪ Varies by system ▪ OUD-CDS implementation date through a predetermined time at which the Wizard interfaces will be turned off in the intervention clinics 
Observation Period
 
 ▪ Varies by patient ▪ Index visit date through a predetermined time at which no more outcome data will be included in the analytic sample

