Hypotheses for Aim 3 predict fewer ED visits (H3.1) and inpatient stays (H3.2) during the observation period of patients receiving care in the OUD-CDS relative to UC clinics. The rate at which each of these outcomes occurs per patient-year will be compared across clinics using generalized estimating equations. Clinic-aggregated counts of ED visits and inpatient stays will be normalized using a Poisson-Normal link function, and the intercept offset by the log of patient-years within the clinic. The model will estimate fixed effects of OUD-CDS, care system and other covariates on the rate of each outcome per patient-year. Should it be feasible, we will also collect and count ED visits and inpatient stays that occurred in the year prior to each patient’s index visit so that treatment group differences in pre-post changes in event rates can be quantified (i.e., treatment by time interaction).

Hypotheses for Aim 4 predict lower healthcare costs and the identification and mitigation of barriers and identification of facilitators to OUD-CDS implementation and uptake. **Analysis of costs** for this aim will include delivery costs of the OUD-CDS and incremental medical care costs attributable to the intervention, defined from the health system perspective. Intervention costs may include resources used for implementation, maintenance, compensation, and PCP and staff training – which may be assessed by interviews/surveys with implementation site staff or study resource use documentation, as appropriate – but will exclude research, development, and measurement costs, using standard micro-cost accounting methods and nationally-representative pricing of inputs. Medical care costs will include all prescribed medications and clinical inpatient, emergency, outpatient, and skilled nursing facility services incurred in the pre- and post-index observation periods by participants in each study group, as indicated by insurance claims and clinical encounter data. The study sample for the cost analysis will be participants who have continuous insurance coverage during the study period, including pharmacy benefits. This sample

will be compared to patients without continuous insurance coverage to assess representativeness and comparative completeness of utilization measurement in comparison to all study participants.

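### The Aim 4 cost analysis keeps only patients with continuous insurance, so H4.1 would be estimated in a sample chosen partly after randomisation

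*Combined protocol and SAP*

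**What the plan says.** The Aim 4 text in Section 13.3 sets the rule: the cost sample is to be "participants who have continuous insurance coverage during the study period, including pharmacy benefits". It adds one check, that this sample "will be compared to patients without continuous insurance coverage to assess representativeness and comparative completeness of utilization measurement". No analysis of all index patients, and none that uses partial coverage, is described.

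The hypothesis has no insurance condition. H4.1 in Section 2.1 says that "patients with OUD or identified as high risk for OUD by the OUD-CDS will have lower healthcare costs in intervention compared to UC clinics". Sections 13.3 and 13.4 take the marginal effect of assignment to an intervention clinic as the estimate of incremental medical cost.

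Table 1 in Section 11.1 gives the cost window as "Observation period, with pre-observation period matched for number of days". Section 10.4 says that eligible patients "will be followed for the duration of the study unless they die or leave the care system". Neither place says what happens in the cost sample when a patient dies or loses coverage part-way.

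**The concern.** Coverage at and before the index visit is settled before the patient can be exposed to the tool. Coverage afterwards is not. Requiring it to be unbroken conditions the comparison on something that happens after randomisation, and discards the covered months of anyone who later loses insurance.

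Two things are at stake. The first is the target: a result in continuously insured patients does not answer H4.1, which concerns everyone eligible. The second is the contrast between arms: if different kinds or numbers of patients leave the sample in each arm, the cost difference mixes the effect of the tool with the effect of selection.

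Aim 3 makes the gap visible. H4.1 expects savings from fewer emergency visits and hospitalisations to outweigh the added costs. Section 13.3 analyses those events with a patient-year offset, so partial follow-up contributes. The same patients can count in Aim 3 and be missing from Aim 4.

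**Working it through.** The plan states no sample size, retention rate or death rate for the cost analysis, so there is no figure to reproduce. The check is a reading of the definitions, followed by two illustrations on assumed inputs.

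**1. Is part of the rule decided after index?** Yes. Section 13.3 counts medical costs in the pre-index and post-index observation periods. A coverage rule that serves that window must reach past the index visit, although the study period itself is undefined.

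**2. Are patients who die excluded?** Section 2.1 gives two definitions of the observation period.

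| Definition | Where | A patient insured until death |
|---|---|---|
| "Index visit date through a predetermined time at which outcome data will no longer be accumulated" | Section 2.1, Definitions | Fails, if coverage must run to the fixed date |
| Index date to the patient's last observation | Section 2.1, H3.1 | Passes |

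The documents do not say which one governs the cost sample.

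**3. How many would the post-index requirement keep?** Assumption: 10% to 25% of patients lose coverage each year, at a constant rate. Section 7.2 sets the lengths. A patient indexed at the end of accrual (October 2022) has about 12 months to October 2023. The earliest HealthPartners patients have 31 months.

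Retained share = (1 − annual loss)^(months/12)

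| Post-index months | 10% annual loss | 25% annual loss |
|---|---|---|
| 12 | 0.90^1 = 0.90 | 0.75^1 = 0.75 |
| 31 | 0.90^(31/12) = 0.76 | 0.75^(31/12) = 0.48 |

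**4. How far could the cost ratio move?** Let q be the share excluded in usual care, RR the intervention to usual-care ratio of exclusion, and k the cost of an excluded patient relative to a retained one, the same in both arms. Let retained patients cost the same in both arms, so the restricted analysis shows a ratio of 1.00. Then

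all-patient ratio = [(1 − q·RR) + q·RR·k] / [(1 − q) + q·k]

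- Deaths excluded, with assumed q of 2-5%, RR 0.8-0.9 and k of 2-5. The largest shift is at q = 0.05, RR = 0.8, k = 5: (0.96 + 0.20)/(0.95 + 0.25) = 1.16/1.20 = 0.967. The smallest is at q = 0.02, RR = 0.9, k = 2: 1.018/1.020 = 0.998.
- Coverage losers excluded, with assumed q of 20-40%, RR 0.8-0.9 and k of 0.5-2. The extremes are at q = 0.4 and RR = 0.8. With k = 2, (0.68 + 0.64)/(0.60 + 0.80) = 1.32/1.40 = 0.943. With k = 0.5, (0.68 + 0.16)/(0.60 + 0.20) = 0.84/0.80 = 1.050.
- With RR = 1, numerator and denominator are equal and the ratio is undistorted.

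The direction depends on k. With fewer exclusions under intervention, the restriction hides a saving if excluded patients are costly and hides an excess if they are cheap.

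**The case against.** The rule has a sound measurement purpose. Section 13.7 reads an absent claim as almost always meaning no utilisation, and that is reasonable only while the patient is covered. Section 13.3 also plans to check representativeness and completeness of capture. The cost model compares pre-index with post-index costs and may adjust for baseline status, which deals with selection explained by those variables. All of this stands, but none of it recovers the post-index costs of the patients removed. Counting costs over covered time serves the same purpose without requiring retention.

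Section 13.3 calls itself an overview and defers to a separate, more detailed Statistical Analysis Plan, which might settle the point. However, it promises more clarity there about the primary outcome analyses, and healthcare cost is a secondary outcome.

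Four stronger readings are tempting, and the documents do not support them.

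- *The rule drops everyone who dies.* No text excludes them, and the two definitions of the observation period give opposite answers. Section 10.4 fits follow-up that ends at death. The supportable statement is that the handling of death is unspecified.
- *Up to 62 months of coverage are at issue* (31 before index plus 31 after). If the matched pre-index window must also be covered, that half is selection on pre-index status, which the remedy below keeps. It should not be charged to this defect.
- *The rule breaks the stated intent-to-treat principle.* Section 10.2 reads "In keeping with an intent-to-treat principle, all index and post-index visits and outcome measures for each patient will be attributed" to the index clinic's arm. It governs arm attribution, which is unchanged in the cost subset, and does not say that every analysis includes every patient. The mismatch is with H4.1 and its interpretation.
- *The intervention sets out to change insurance or employment.* No aim concerns either. Treatment initiation and maintenance are aims, and all-cause mortality is a listed secondary outcome, so an arm difference in who stays in the sample is possible but not shown.

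**Conclusion.** The concern holds in a limited form. The cost sample depends partly on coverage after randomisation, over a window the documents do not define. H4.1 would therefore be estimated in a narrower group than it names, and no planned analysis corrects for that.

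The loss of sample could be substantial: at an assumed 10-25% annual loss, 10-25% of patients would be removed by 12 months and 24-52% by 31 months. Bias in the arm comparison is possible but not demonstrated. It needs coverage loss or death, or the costs of those excluded, to differ by arm. Under the assumed inputs above, a restricted ratio of 1.00 could stand for an all-patient ratio of 0.967-0.998 (deaths) or 0.943-1.050 (coverage loss). Those ranges come from a simple model with a common k and show scale only; they do not predict this trial's error.

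This is a secondary outcome. The change is still worth making, because a better method is cheap and its logic is already used for Aim 3.

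**What to change.** Amend the Aim 4 text in Section 13.3, or the separate Statistical Analysis Plan, as follows.

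1. Define the cost cohort by medical and pharmacy coverage at index and in a stated pre-index window only. Replace the undefined study period with dates, and say which observation-period definition applies.
2. Count costs over covered time from index until death, disenrolment or end of data. Treat death as the end of cost accrual, with zero cost afterwards, and not as a reason for exclusion.
3. Handle disenrolment with inverse-probability-of-censoring weights built from baseline and accruing covariates. A covered-time offset, parallel to the Aim 3 patient-year offset, is a simpler alternative. The two are not equivalent, so name one as the main analysis in advance.
4. Report coverage loss and death by arm.
5. Keep the continuous-coverage sample as a sensitivity analysis, together with the planned comparison with other patients.

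The cost is revised wording and modest programming, with no new data collection for the patients in this cohort. The downside is reliance on a censoring assumption. The weights need coverage loss to be explained by the measured covariates. The offset needs it to be unrelated to cost level, which fails if people lose coverage at high-cost times.

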2.6 Analyses

Aims 1 through 3 pertain to the effectiveness of the OUD-CDS intervention relative to UC, predicting that it will increase diagnosis, naloxone prescribing, and access to MOUD, and

[figure not shown]
decrease ED visits and inpatient hospital stays. These hypotheses will be tested using generalized linear mixed models to account for clustering of outcomes within eligible patients and randomized clinics or generalized estimating equations to compare event rates across clinics. Outcomes will be normalized via distribution-appropriate link functions (e.g., logistic-Normal, Poisson-Normal). Clinic-randomized treatment group, care system and other predictors will be treated as fixed effects.

For Aim 4, OUD-CDS implementation and maintenance costs will include programming, training and ongoing algorithm maintenance but exclude research costs, using micro-cost accounting methods and nationally-representative pricing of inputs. A generalized linear model, allowing clustering by clinic and controlling for demographics and baseline clinical risk factors, will estimate costs by study arm to account for the skewed distribution of costs.[1-3] Economic analyses will be done in consultation with the NIDA P-30 CHERISH program.

The Aim 5 mixed methods analysis will include an iterative, team-based, triangulation of quantitative and qualitative data sources. Qualitative analysis of the field notes, observations and interviews will be conducted using techniques of qualitative content analysis based on a deductive-directed approach to evaluate the factors influencing RE-AIM constructs.[4]

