13.0 STATISTICAL DESIGN AND ANALYSES

13.1 General Design

13.1.1 Study Hypotheses

H1.1: Patients previously undiagnosed with OUD but identified as high risk by the OUD-CDS at an index visit will be more likely to receive an OUD diagnosis (in the problem list or as an ICD-10 visit code) in intervention clinics than UC clinics within 30 days post-index.

H1.2: Patients previously diagnosed with OUD or identified as high risk by the OUD-CDS at an index visit will be more likely to have naloxone rescue kits ordered in the intervention clinics than in the UC clinics within 30 days post-index.

H2.1: Patients identified as having OUD or as being at high-risk for OUD by the OUD-CDS at an index visit will be more likely to have MOUD orders or referral for OUD treatment within 30 days post-index in intervention clinics than in UC clinics.

H2.2: Patients identified as having OUD or as being at high-risk for OUD by the OUD-CDS at an index visit will have significantly more days covered by a MOUD prescription at 90 days post-index in intervention clinics than in UC clinics.

H3.1: Patients with OUD or identified as high-risk for OUD by the OUD-CDS who are cared for in intervention clinics will have significantly fewer post-index ED visits during the observation period (i.e., the period between each patient's index date and last observation) compared to patients cared for in UC clinics.

H3.2: Patients with OUD or identified as high-risk for OUD by the OUD-CDS who are cared for in intervention clinics will have significantly fewer post-index hospitalizations during the observation period compared to patients cared for in UC clinics.

H4.1: After controlling for demographics, baseline clinical status and prior costs of care, patients with OUD or identified as high risk for OUD by the OUD-CDS will have lower healthcare costs in intervention compared to UC clinics during the observation period (i.e., savings from lower ED visits and hospitalizations will outweigh increased costs of OUD treatment and naloxone rescue kits and OUD-CDS implementation and maintenance).

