13.1.2 Primary and Secondary Outcomes (Endpoints)

Primary outcome measures will include:

1. OUD diagnosis (in the problem list or as an ICD-10 visit code) within 30 days of index visit for patients identified by the OUD-CDS as being at high risk of OU
2. Naloxone prescription within 30 days of index visit for patients with OUD or identified by the OUD-CDS as being at high risk for OUD
3. MOUD orders or referral to OUD treatment within 30 days of index visit for patients with OUD or identified by the OUD-CDS as being at high risk for OUD
4. Total days covered by an MOUD prescription in the 90 days after index visit for patients with OUD or identified by the OUD-CDS as being at high risk for OUD

Secondary outcome measures will include:

1. OUD diagnosis (in the problem list or as an ICD-10 visit code) at index or within 90 days of index visit for patients identified by the OUD-CDS as being at high risk of OUD
2. Naloxone prescription at index or within 90 days of index visit for patients with OUD or identified by the OUD-CDS as being at high risk for OUD
3. MOUD orders or referral to OUD treatment at index or within 90 days of index visit for patients with OUD or identified by the OUD-CDS as being at high risk for OUD
4. Number of ED visits during the observation period for patients with OUD or identified by the OUD-CDS as being at high risk for OUD
5. Number of hospitalizations during the observation period for patients with OUD or identified by the OUD-CDS as being at high risk for OUD
6. Healthcare costs during the observation period for patients with OUD or identified by the OUD-CDS as being at high risk for OUD, compared with healthcare costs over the same interval preceding the observation period
7. Cost of OUD-CDS implementation and maintenance
8. All-cause mortality rates during the observation period for patients at high risk of OUD
9. Fatal and non-fatal opioid overdoses during the observation period for patients at high risk of OUD
10. Rates of OUD-CDS use in intervention clinics
11. PCP ratings of confidence in treating patients with OUD prior to go-live date and 9-months following go-live date
12. Intervention clinic PCP ratings of satisfaction and acceptability of the OUD-CDS at 9 months following go-live date

Exploratory outcome measures may include:

1. Number of non-waivered PCPs becoming buprenorphine waived during the intervention period, assessed via health system administrative data

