Paid amounts for medical claims that are specific to medical groups and insurance plans may provide a biased view of costs between pre- and post-intervention periods. To address this, claims will be converted to dollar amounts using Total Care Relative Resource Values™ (TCRRVs), which are a nationally standardized set of measures that have been endorsed by the National Quality Forum[50] and are derived from Centers for Medicare and Medicaid Services (CMS) relative value units (RVUs). TCRRVs extend CMS RVU measures to include utilization categories, such as laboratory services and medications, which do not have CMS RVU weights.[51] Inpatient costs are calculated by applying TCRRVs to the diagnosis-related group classification and length of stay of the hospitalization.

Standard health econometric and specification testing methods will be used to assess the incremental differences in healthcare costs between study groups [1, 2, 39]. Specifically, healthcare care costs will be analyzed using a generalized hierarchical model with a time x study group interaction term that can account for clinic-level clustering and the correlation in each subjects' repeated measures of costs over time (i.e., pre-index and post-index). Demographics and baseline clinical status will be controlled for based on randomization imbalances and model fit criteria. The marginal effect of being assigned to an intervention clinic will provide an estimate of the incremental medical cost associated with the OUD-CDS intervention. To account for the non-normality in costs, the distribution family will be specified appropriately, such as by using the modified Park test,[2] and the goodness of fit for the specified link function will be tested, such as by using modified Hosmer and Lemeshow and Pregibon link tests.[53, 54] Confidence intervals will be estimated using heteroscedasticity-robust estimation methods.[55]

Mixed method data analysis for Aim 5 will occur rapidly as data are collected, so that new information can support decision making about revisions in the implementation plan and adaptations as the study proceeds. All data analysis and subsequent conclusions and decisions made during live implementation will be carefully documented.

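### The H4.1 cost model treats prior cost as a repeated outcome and leaves the arm contrast unnamed; adjusting post-index cost for prior cost at patient and clinic level would be more precise with the same data

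*Combined protocol and SAP*

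**What the plan says.** Four places describe the cost analysis, and they differ.

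- **Section 13.1.1 (H4.1)** compares observation-period cost between arms "After controlling for demographics, baseline clinical status and prior costs of care".
- **Section 13.1.2 (secondary outcome 6)** defines the outcome as observation-period cost "compared with healthcare costs over the same interval preceding the observation period". Table 1 in Section 11.1 agrees: "Observation period, with pre-observation period matched for number of days".
- **Section 13.3 (Aim 4)** specifies that "healthcare care costs will be analyzed using a generalized hierarchical model with a time x study group interaction term", allowing for clustering by clinic and for the correlation of each patient's "repeated measures of costs over time (i.e., pre-index and post-index". On covariates it says: "Demographics and baseline clinical status will be controlled for based on randomization imbalances and model fit criteria". Prior cost is not among them. The estimate is described thus: "The marginal effect of being assigned to an intervention clinic will provide an estimate of the incremental medical cost associated with the OUD-CDS intervention".
- **Section 2.6** says: "A generalized linear model, allowing clustering by clinic and controlling for demographics and baseline clinical risk factors, will estimate costs by study arm". It has neither a time term nor prior cost.

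Section 13.4 tests H4.1 two-sided at 0.05. No section gives a sample size, SD, pre/post correlation or power for cost.

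**The concern.** Clinics are randomised, so the arms have the same expected pre-index cost, and any observed baseline difference is chance. A time by group interaction with free baseline means subtracts that chance difference in full. Regressing post-index cost on prior cost subtracts only the part that predicts later cost. If the unnamed marginal effect is instead the post-period contrast of the same unconstrained model, prior cost contributes essentially nothing to its precision.

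Cost is highly skewed, and H4.1 is analysed only in patients with continuous insurance coverage, a subset of unstated size. Precision is therefore likely to be scarce. The four descriptions also leave the analyst to choose the model and contrast after seeing the data.

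**Working it through.** There is no stated H4.1 figure to reproduce, so the check compares the variances of the candidate estimators on a linear scale, with equal pre and post variance.

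**Inputs from the documents.** At least 30 clinics, about 1:1 (Sections 13.2.1 and 6.1). A minimum of 50 patients per clinic (Section 13.2.2). More than 10,000 patients expected (Section 14.3.1), so about 10,000/30 = 333 per clinic before the insurance restriction. The power section's ICCs of 0.01, 0.03 and 0.05 are for process measures, not cost.

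**Assumptions.** Cost ICC 0.02 to 0.03; patient pre/post correlation rw 0.3 to 0.5; clinic pre/post correlation rb 0.5 to 0.95; m = 50 to 333 patients per clinic.

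**Step 1: one correlation r, no clustering.** Relative to comparing post-index cost alone (variance 1), the interaction has variance 2(1 − r) and adjustment has 1 − r². Their ratio is 2/(1 + r): 1.54, 1.33 and 1.18 at r = 0.3, 0.5 and 0.7. The interaction is worse than ignoring baseline when r is below 0.5.

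**Step 2: clusters.** Let B = ICC and W = (1 − ICC)/m. Up to a common factor:

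- post-only: B + W
- interaction: 2B(1 − rb) + 2W(1 − rw)
- adjustment with a patient-level slope only: B(1 + rw² − 2·rw·rb) + W(1 − rw²)
- adjustment at patient and clinic-mean level: (B + W)(1 − e²), where e = (B·rb + W·rw)/(B + W)

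The interaction over adjustment at both levels is then 2/(1 + e).

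Example: ICC 0.03, m = 100, rw 0.3, rb 0.5. B = 0.03, W = 0.0097, sum 0.0397. Interaction = 0.0300 + 0.0136 = 0.0436, or 1.10 of post-only. Patient slope = 0.0237 + 0.0088 = 0.0325, or 0.82. e = 0.0179/0.0397 = 0.451, so both levels = 1 − 0.451² = 0.80. Ratio 2/1.451 = 1.38.

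| ICC | m | rw | rb | interaction / post-only | interaction / patient slope only | interaction / both levels | post-only / both levels |
|---|---|---|---|---|---|---|---|
| 0.02 | 50 | 0.3 | 0.5 | 1.20 | 1.41 | 1.43 | 1.19 |
| 0.03 | 100 | 0.3 | 0.5 | 1.10 | 1.34 | 1.38 | 1.26 |
| 0.02 | 100 | 0.3 | 0.7 | 0.86 | 1.15 | 1.28 | 1.48 |
| 0.02 | 333 | 0.5 | 0.7 | 0.65 | 1.13 | 1.19 | 1.83 |
| 0.02 | 333 | 0.3 | 0.85 | 0.44 | 0.71 | 1.12 | 2.55 |
| 0.03 | 100 | 0.3 | 0.95 | 0.42 | 0.68 | 1.12 | 2.67 |
| 0.03 | 333 | 0.5 | 0.95 | 0.18 | 0.53 | 1.05 | 5.83 |

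The first and last rows are the extremes of the interaction / both levels column over the assumed ranges: 1.05 to 1.43. The last column is the loss if the marginal effect means the unconstrained post-period contrast.

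**Step 3: power.** If adjustment at both levels had 80% power, the interaction would have Φ(2.80/√1.43 − 1.96) = 65% at the worst corner and Φ(2.80/√1.05 − 1.96) = 78% at the best.

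**Step 4: price of the extra slope.** With 30 clinics and terms for intercept, arm and two system indicators, 26 degrees of freedom remain. Estimating one clinic-level slope inflates the variance by about 1/(26 − 2) = 4% on average. That roughly cancels the gain at 1.05, but not in the other rows.

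**Step 5: skewness.** In simulated lognormal costs (30 clinics of 100, ICC 0.03, log SD 1.2), variance relative to post-only was 1.26 for the interaction against 0.81 for a gamma log-link model with log prior cost (patient r 0.3, clinic r 0.5 on the log scale). At patient r 0.5 and clinic r 0.9 it was 0.67 against 0.47. The direction agrees. The size depends on the family and link, which Section 13.3 leaves to be chosen by test.

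**The case against.** The strongest reply is that Section 13.3 never says the effect is read from the interaction. It names a marginal effect, without a contrast and without saying that baseline means are free. That is correct, so a reader who infers that the plan is definitely a difference-in-differences goes further than the text. But the post-period contrast of an unconstrained model also loses precision. Only an equal-baseline constraint avoids the loss, and no section states one.

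Second, outcome 6 and Table 1 do define cost as pre versus post, and H4.1 names no method of control. The pre/post model is therefore a legitimate reading of the plan, and calling it a departure from H4.1 would be too strong. What stands is that the sections do not agree on one model.

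Third, clustering changes the sizes. A reader might infer from the single-correlation formula that the planned model is worse than ignoring prior cost, or that power falls from 80% to 62%, 68% or 73% (r = 0.3, 0.5, 0.7). The documents give no correlations to support either. With moderately stable clinic costs the interaction beats post-only (0.86 in the third row). With large clinics and stable clinic costs it also beats a patient-level slope (0.71 in the fifth row).

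Fourth, continuous coverage during the study period (Section 13.3) is met after randomisation, so equal expected baseline cost in the cost sample is likely but not guaranteed. That is a reason to keep the pre/post estimate as a sensitivity analysis.

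Finally, Section 13.3 calls itself an overview and defers detail to a Statistical Analysis Plan. That deferral stresses the primary outcome analyses, and the only cost model in these documents is the one described.

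**Conclusion.** The point holds as one of efficiency and consistency. As written, either reading of the H4.1 estimate is less precise than adjustment for prior cost at patient and clinic-mean level. Under the assumed ranges the interaction's variance is about 1.05 to 1.43 times as large, before the roughly 4% cost of the extra slope; the post-period reading loses 1.19 times or more. With very stable clinic costs the gain over the interaction is close to nil. All sizes rest on assumed correlations, ICC and clinic sizes, equal pre and post variance, and free baseline means. A reader might infer that the planned estimate is biased; nothing in the documents shows that. The outcome is secondary, no power is claimed for it, and the change is worth making because it is nearly free.

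**What to change.** In Section 13.3, name one primary H4.1 contrast: the arm difference in mean post-index cost, adjusted for pre-index cost at both patient and clinic-mean level, with care system as a fixed effect and clinic as the cluster. Use a transform of prior cost that admits zeros, such as the log of cost plus one. An acceptable alternative is the stacked pre/post model with pre-index means constrained equal across arms and clinic-by-period random effects.

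Keep the time by group estimate as a sensitivity analysis. It stays true to the pre/post wording of outcome 6 and covers baseline differences that the continuous-coverage restriction might introduce. Then bring Sections 2.6, 13.1.1, 13.1.2 and 13.3 to the same model and contrast, along with the repeats of H4.1 and outcome 6 in Sections 2, 5 and 7.

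The cost is wording plus one or two extra slopes estimated with about 30 clinics. The pre-index costs are already to be collected.
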